8.4.3 Hypothesis Testing

Unless otherwise stated, all significance testing will be 2-sided at the significance level of 0.05.

9.0 Analysis Sets

Analyses	Enrolled	Randomized	Treated per protocol	Safety
Disposition	✓			
Baseline Characteristics		✓	✓	
Safety Assessments				✓
Primary Efficacy Analysis			✓	
Other Efficacy Analysis			✓	
PK Analysis			✓	

9.1 Enrolled

All participants who sign informed consent.

9.2 Randomized

All randomized subjects who have started study drug infusion in at least one treatment period. This is also known as the Intent to Treat (ITT) population. Data in this data set will be analyzed based on randomized sequence of treatments.

9.3 Treated (per protocol)

All randomized participants who were given both study treatments and completed the study as per protocol. Participants will be included in the treatment group they received in each period.

9.4 Safety

All randomized participants who take at least 1 dose of double-blind study treatment. Participants will be included in the treatment group they received in each period.

10.0 Subject Disposition

The number of subjects in each analysis set will be presented.

The number and percentage of subjects who withdrew from the study prematurely and a breakdown of the corresponding reasons for withdrawal will be presented by analysis set. Percentages will be based on the total number of subjects in the analysis set.

11.0 Protocol Deviations

Protocol deviations will be collected and entered into the Clinical Trial Management System (CTMS) per clinical monitoring Standard Operating Procedures. From CTMS, protocol deviations will be pulled into SDTM. Important protocol deviation data will be listed by subject.

12.0 Demographic and Baseline Characteristics

12.1 Demographics

Subject demographics will be summarized descriptively for the Randomized and Per Protocol analysis sets. The summary will include the subjects' age (years), sex, race, ethnicity, weight (kg), height (cm), and BMI (kg/m²). Any measurements will be included from assessments performed during the Screening Visit. .

All demographic data, as collected during the screening visit, will be listed by subject.

12.2 Medical History

Medical history including disease under study will be categorized by preferred term according to the Medical Dictionary for Regulatory Activities (MedDRA) and will be listed by subject.

12.3 Other Baseline Characteristics

All screening criteria data collected on the CRF (including failed eligibility criteria) will be listed by subject.

Childbearing Potential will be listed.

14.0 Treatment Compliance and Exposure

The number and percentage of subjects receiving full dose of study drug will be summarized by sequence in periods 1 and 2 for the safety analysis set.

All study drug administration data will be listed by subject.

15.0 Efficacy Analyses

15.1 Effect of BMS-986231 on urine output

All primary efficacy analyses will be performed using the treated (per protocol) population.

Urinary output will be listed by timepoint.

The volumes (total within 4 h after furosemide dosing, total within 4 h before furosemide dosing, total within 8 h after start of BMS-986231/placebo dosing and difference of totals after and before furosemide dosing) after BMS-986231 and after placebo will be calculated per patient.

Descriptive statistics (n, mean, SD, %CV, median, min, and max) will be used to summarize the absolute difference between the volumes under BMS-986231 dosing and under placebo and the percent change from placebo under BMS-986231 dosing of urinary output by treatment.

Plots of the arithmetic mean urinary output + SD by scheduled sampling times will be provided by treatment. Bar plots showing the arithmetic mean urinary output and the individual urinary output by interval and treatment will be provided. These plots will show time in hours. The plots will match the summary table results. Plots will be presented to the last scheduled time point.

A within patient analysis using a paired T-test will be performed to compare the volumes of urinary excretion and to test if there is a significantly different amount of urine secreted while receiving BMS-986231 versus placebo. Body weight might be considered as covariate, if significant.

The SAS PROC TTEST code is as follows:

```
proc ttest data = volume;  
  PAIRED BMS-986231*placebo;  
run;
```

Paired profiles and Q-Q plot of the urinary output under BMS-986231 and placebo treatment will be provided for a visual representation of the data.

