Study participants will be admitted to the study facility the day before or on the treatment day, according to local practice and patient preferences. Assessment of symptoms and signs of HF, including body weight, vital signs and laboratory tests will be performed pre-dose (before start of infusion). On each treatment day, blood pressure and HR should be within the inclusion / exclusion criteria limits prior to study drug administration. The study drug infusion could start without waiting for the results of the laboratory assessments done in the morning of the treatment day at the study facility if the following criteria are met:

- The results of the laboratory assessment at screening / previous period are within ranges compatible with inclusion criteria,
- The study participant was medically stable with no signs of overt HF decompensation or deteriorating signs and symptoms of congestion and without change in medication since the screening visit / previous period.

If the laboratory tests (e.g. electrolytes, serum creatinine, estimated glomerular filtration rate (eGFR), hemoglobin, transaminases) on the morning prior to infusion, are not within inclusion and exclusion criteria limits, the study drug could be interrupted / discontinued after consultation with the Medical Monitor. The abnormalities should be corrected before the next treatment period.

Physical examinations, vital sign measurements, 12-lead ECG and urinary output will be performed at selected times throughout the dosing interval. Participants will be closely monitored for AEs throughout the study. Blood samples will also be collected at selected intervals after start of study drug administration for PK analysis and biomarkers.

Prior to start of the infusion, study participants will be asked to void and urine collected. A bladder scan can be performed to ensure adequate bladder emptying. Patients will be asked to void at least every 2 hours during the first 4 hours post-start infusion and before furosemide bolus, and at least hourly from 4 to 8 hours post-start infusion. At 8 hours after start of study drug infusion, just before study drug discontinuation, a void will be done, collected and recorded and a second bladder ultrasound can be performed to ensure adequate bladder emptying. Urine will be collected until 2 hours after the study drug discontinuation.

Discharge

[figure not shown]

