6.1 Sample Size Considerations

The number of subjects to be enrolled was chosen based on practical considerations. Twenty patients with HFrEF will be randomized to one of 2 sequences: BMS-986231/furosemide followed by placebo/furosemide or placebo/furosemide followed by BMS-986231/furosemide. The difference between BMS-986231 and placebo in total urine output in the 4 hours following furosemide administration will be estimated and presented with 95% confidence intervals (CIs).

Normal healthy volunteers have a urinary output around 0.5-1.0 mL/kg/H (40-100 mL/H), which could be decreased in people over 65 years old or patients with HF at around 0.2-0.5 mL/kg/H (20-40 mL/H). Patients with HF given a bolus of IV loop diuretics is estimated to have their diuresis increased to 250-300 mL/H in the 4 hours following the administration. Assuming the standard deviation of urine output change is 20~35 mL/H based on the estimated range of the changes, with 20 patients, the study will be able to demonstrate a 20% increase in urinary output compared to placebo, with 90% power.

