6.2 Randomization

The subjects were randomized by the Biostatistics Department of the EDS group of PRA Health Sciences using PROC PLAN in SAS. Subjects (N=20 plus 4 additional) were assigned to one of the two sequences active treatment/placebo or placebo/active treatment with a 1:1 allocation ratio. An additional randomization was run a second time for the second site (Richmond, London) which was only added to the study when it was already running at the first site (NHS, Glasgow). For details, please see Global Note to File no.2.

Subject numbers that were used are R01-R24 and S01-S24. Participants will not be replaced if they are discontinued from the study.

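### The primary paired t-test in this randomised 2x2 crossover has no period term; adding one costs one degree of freedom, tightens the 95% CI if the periods differ, and removes the shift in the estimate that unequal sequences would cause

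*SAP*

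**What the plan says.** Patients are randomised 1:1 to BMS-986231 then placebo, or the reverse, with 7 days to 4 weeks between two one-day periods (SAP 6.0 to 6.2).

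- **Primary test.** SAP 15.1: "A within patient analysis using a paired T-test will be performed to compare the volumes of urinary excretion". The code is `PROC TTEST` with only a `PAIRED` statement. Protocol 9.4.1.1 and SAP 15.2 (FeNa, FeK) use the same test.
- **Covariates.** SAP 8.4.2 predetermines none. SAP 15.1 leaves body weight open as a covariate if it proves significant. Period and sequence are not mentioned.
- **Planned estimate.** SAP 6.1 promises the treatment difference in 4-hour urine output with a 95% CI in 20 patients. Its variability input is: "Assuming the standard deviation of urine output change is 20~35 mL/H based on the estimated range of the changes".
- **Sequence and period elsewhere.** SAP 14.0 says full-dose counts "will be summarized by sequence in periods 1 and 2 for the safety analysis set", so both variables are available. No readable efficacy analysis uses them.
- **Sequence balance.** SAP 6.2: "An additional randomization was run a second time for the second site", and "Participants will not be replaced if they are discontinued from the study". No block size is given. The primary set (SAP 9.3) is: "All randomized participants who were given both study treatments and completed the study as per protocol".

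**The concern.** A two-period crossover confounds treatment with period within each patient; randomising the order lets the analysis separate them. The pooled paired test does not use that information. A period difference goes into the error term and, if the sequences end with unequal completers, partly into the estimate. Readers would have no way to see it.

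Neither document reports a period effect. One route is written into the plan: when treatment-day laboratory values are outside the limits, Protocol 4.1 says "The abnormalities should be corrected before the next treatment period". That change runs only from period 1 to period 2. It shows that a period difference is possible; it says nothing about its size or direction.

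At stake are the width and, conditionally on the split, the centre of the interval that is the study's main result.

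**Working it through.** **Inputs.** N = 20, SD of the within-patient difference 20 to 35 mL/H, diuresis 250 to 300 mL/H and a 20% increase (SAP 6.1), so the target is 50 to 60 mL/H; two-sided 0.05 (SAP 8.4.3). Period shifts of 10, 25 and 50 mL/H are assumptions; 50 equals the whole target and is a stress case.

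**The plan's own figure.** A paired t-test with n = 20, difference 50 and SD 35 has power 99.998%. The stated 90% is met but not reproduced: it would need an SD of about 65 mL/H (difference 50) or 78 (difference 60). SD 65 is used below only as a stress value; it is not in the documents.

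**Model.** Let σ be the SD of the difference, τ the treatment effect and π the period difference. The BMS-minus-placebo differences have mean τ + π in one sequence (a completers) and τ − π in the other (b completers), with N = a + b.

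- Paired estimate: mean τ + π(a − b)/N. Expected variance estimate: σ² + π² × 4ab/[N(N − 1)], on N − 1 df.
- Period-adjusted estimate: mean τ, variance σ² × ¼(1/a + 1/b), on N − 2 df.

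**Break-even for CI width.** Set the expected squared half-widths equal. At 10:10, 4ab/[N(N − 1)] = 400/380 = 20/19, so t₁₈² = t₁₉²(1 + (20/19)(π/σ)²). With t₁₈ = 2.1009 and t₁₉ = 2.0930, π/σ = √{[(2.1009/2.0930)² − 1] × 19/20} = 0.085.

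| Completers | Break-even (SD units) | At SD 35 (mL/H) | Shift of the paired estimate |
|---|---|---|---|
| 10:10 | 0.085 | 3.0 | 0 |
| 11:9 | 0.13 | 4.6 | 10% of π |
| 12:8 | 0.22 | 7.7 | 20% of π |
| 13:7 | 0.33 | 11.7 | 30% of π |

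For example, at 12:8 with π = 25 the estimate moves 0.20 × 25 = 5 mL/H, or 20 mL over 4 hours against a target of 50 × 4 = 200 mL. Averaged over randomisation the bias is zero.

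**Mean 95% CI width at 10:10 (mL/H).**

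| SD | Paired, π = 10 | π = 25 | π = 50 | Adjusted, any π |
|---|---|---|---|---|
| 20 | 21 | 30 | 51 | 19 |
| 35 | 34 | 40 | 58 | 32 |

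With no shift at SD 35 the paired interval is slightly narrower: 32.3 against 32.4.

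**Type I error of the paired test.** At most 5.0% at 10:10, 11:9 and 12:8. At 13:7, for π = 10 / 25 / 50, it is 6.6 / 7.0 / 2.5% at SD 20 and 5.6 / 7.3 / 6.5% at SD 35. The adjusted test stays at 4.8 to 5.1% in simulation.

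**Power for 50 mL/H at the plan's SDs.** At 10:10 the paired test keeps at least 99.3% for every shift. At SD 35 with an adverse shift of 50 it falls to 97% (11:9), 91% (12:8) and 80% (13:7), against 99.99% adjusted. With an adverse shift of 25 it stays at or above 99.6%.

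**Chance of imbalance at randomisation**, assuming 10 patients per site. If each 24-number list is unblocked, 12:8 or worse has probability 39% and 13:7 or worse 15%. With blocks of 4 to 12 these are 6 to 10% and 0%. Non-completion adds to this: from 10:10, two random losses leave 10:8 with probability 47%.

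**The case against.** The paired t-test is prespecified in both documents and, at 10:10, is valid and conservative. At the plan's SDs no planned conclusion is in danger unless a shift as large as the target effect coincides with unequal sequences, and type I error rises only at 13:7. Several design features work against a large period effect: stable background therapy at entry, a washout of at least 7 days, and the similar diet, fluid cap and standardised meals of Protocol 5.3.1. Patients whose laboratory values needed correction may not reach the per-protocol set at all. The imbalance probabilities rest on assumed block sizes and site numbers; SAP 6.2 points to a note to file that is not part of these documents. For small shifts adjustment gains nothing: at 12:8 the paired estimate has the lower mean squared error up to 0.23 SD (8 mL/H at SD 35). On this view a sensitivity analysis is enough.

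All of these facts stand, and they limit the point to an improvement. They do not reverse the balance of costs: the adjusted analysis loses very little when there is no period effect and protects width and centre when there is one. Nobody can tell in advance which case applies, because the documents give no estimate of the period difference.

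On body weight, SAP 8.4.2 speaks only of predetermined covariates, so the optional wording in SAP 15.1 is not strictly contradictory. It is still absent from the printed code. Its effect is immaterial: entered only if significant and centred, it gives a type I error of 5.2%.

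**Conclusion.** The point holds. The primary analysis ignores the randomised sequence, and nothing readable elsewhere makes up for it. At 10:10 the consequence is loss of precision once the period difference passes about 0.085 SD (1.7 to 3.0 mL/H at the plan's SDs), small at first: 2.8% wider at 0.25 SD and 12% wider at 0.5 SD. With unequal completers there is also a conditional shift of 10 to 30% of the period difference between 11:9 and 13:7. The larger losses need an assumed 50 mL/H shift together with imbalance. The change should be made because it is inexpensive and protects the reported interval, not because the planned test is invalid.

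**What to change.** In SAP 15.1 make the period-adjusted analysis primary: compare within-patient period differences between the two sequences or, equivalently, fit patient, period and treatment as fixed effects.

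```
proc glm data=volume;
  class subj period trt;
  model vol = subj period trt;
  lsmeans trt / pdiff cl;
run;
```

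If `PROC MIXED` with a random patient effect is preferred, add `NOBOUND`; the two agree only when the between-patient variance is not truncated at zero. Report the adjusted difference with its 95% CI and the number of completers per sequence, and keep the paired t-test as supportive. Use the same model for FeNa and FeK in SAP 15.2. Record the change in SAP 7.1, which now declares none, before database lock. As a tidy-up, delete the body-weight sentence.

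**Cost.** SAP wording, a few lines of SAS, no new data and one degree of freedom. With no period effect the CI at 10:10 is about 0.4% wider, and at SD 20 to 35 the power loss is below 0.01 percentage points. At the stress SD of 65, power falls from 90.3% to 90.2% at 10:10, 89.0% at 12:8 and 87.3% at 13:7.

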15.2 Effect of BMS-986231 on fractional excretion

Secondary efficacy analyses will be performed using the per protocol population.

The fractional excretion (total within 4 h after furosemide dosing, total within 4 h before furosemide dosing, total within 8 h after start of BMS-986231/placebo dosing and difference of totals after and before furosemide dosing) of Na (FeNa) and K (FeK) after BMS-986231 and after placebo will be calculated per patient.

Descriptive statistics (n, mean, SD, %CV, median, min, and max) will be used to summarize the absolute difference between the excretion under BMS-986231 dosing and under placebo and the percent change from placebo under BMS-986231 dosing of fractional excretion by treatment.

Bar plots showing the arithmetic mean urinary output and the individual urinary output by interval and treatment will be provided.

A within patient analysis using a paired T-test will be performed to compare the volumes of urinary excretion and to test if there is a significantly different amount of urine secreted while receiving BMS-986231 versus placebo.

Paired profiles of fractional excretion will be provided for a visual representation of the data.

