After a dose reduction, the dose cannot be increased again. Study drug will be permanently discontinued after it has been down titrated once, and criteria for dose reduction or interruption has been met again.

If an infusion in a given period is discontinued, patients remain eligible to complete the subsequent period.

Any decision to lower the dosage level of study drug or discontinue study drug should be based on the investigator's assessment of the patient's overall clinical stability, in the context of appropriate ongoing monitoring of the patient's condition.

A 50% dosage adjustment downward will be achieved by decreasing the rate of study drug infusion from 20 mL/H to 10 mL/H.

Furosemide will be administered through an IV bolus injection at H4 of study drug infusion. In the event the study drug has been reduced, furosemide injection is administered at H4 as planned. If the study drug has been temporarily interrupted, then restarted, furosemide will be administered after at least 4 hours of effective study drug infusion.

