8.1.2 Fractional Excretion of Na (FeNa) and K (FeK)

The plasma and urine concentrations of Na and K will be measured at the time points in the Schedule of Activities (Section 1.3), in [Table 7](#) (blood sampling time points) and in [Table 8](#) (urine collection intervals). The FeNa (%), FeK (%) and the concentration ratio of urinary sodium to urinary furosemide after the 40 mg furosemide bolus (collected 4-8 hours post-start infusion) will be compared to baseline (4-8 hour levels post-start infusion placebo period).

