9.3.2 Secondary Endpoints

- FeNa, FeK, furosemide urinary and plasma concentration and ratio urinary sodium to urinary furosemide at 8 hours post-start infusion. Parameter values while patient is on BMS-986231 compared to placebo: absolute differences and % change from placebo.

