9.4.1.2 Secondary Efficacy Analysis

Secondary efficacy analyses will be performed using the randomized population. The FeNa, FeK, furosemide urinary and plasma concentration and the ratio of urinary sodium to urinary furosemide will be calculated at each time point over 4-hour urine/plasma collection after a bolus injection of 40 mg furosemide while receiving BMS-986231 or placebo. All data will be listed and tabulated. Graphical presentations may be provided.

A similar analysis as described in the primary efficacy analysis section will be conducted on the values derived at the 8-hour time point (8 hours after start of infusion).

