5.2.1 Secondary Endpoints

FeNa, FeK, furosemide urinary and plasma concentration and ratio urinary sodium to urinary furosemide at 8 hours post-start infusion. Parameter values while patient is on BMS-986231 compared to placebo: absolute differences and % change from placebo.

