15.3 Effect of BMS-986231 on furosemide concentration

Furosemide urinary and plasma concentrations and the ratio of urinary sodium to urinary furosemide will be calculated at each time point over 4-hour urine/plasma collection after a bolus injection of 40 mg furosemide while receiving BMS-986231 or placebo

Descriptive statistics (n, mean, SD, %CV, median, min, and max) will be used to summarize the absolute difference and the percent change from placebo of furosemide urine concentration, furosemide plasma concentration and the ratio of urinary sodium to urinary furosemide at 8 h by treatment.

Paired profiles of furosemide urine concentration, furosemide plasma concentration and the ratio of urinary sodium to urinary furosemide (4 h after furosemide dosing) will be provided for a visual representation of the data.

[REDACTED]

[REDACTED]

[REDACTED]

[REDACTED]

[REDACTED]

[REDACTED]

[REDACTED]

[REDACTED]

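### The SAP does not carry through the protocol's secondary analyses at 8 h (FeNa/FeK time point and tested quantity, three paired tests, analysis population), yet SAP 7.1 declares no changes

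*SAP*

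**What the plan says.** - **Endpoint and time.** Protocol 9.3.2 lists "FeNa, FeK, furosemide urinary and plasma concentration and ratio urinary sodium to urinary furosemide at 8 hours post-start infusion". SAP 5.2.1 gives the same list and the same time.
- **Analysis.** Protocol 9.4.1.2 states: "A similar analysis as described in the primary efficacy analysis section will be conducted on the values derived at the 8-hour time point". The section it points to, Protocol 9.4.1.1, contains summaries, tabulation and one inferential method, a within-patient paired t-test.
- **A second time definition.** Protocol 8.1.2 compares FeNa, FeK and the sodium/furosemide ratio in urine "collected 4-8 hours post-start infusion".
- **SAP 15.2.** For each ion it derives "The fractional excretion (total within 4 h after furosemide dosing, total within 4 h before furosemide dosing, total within 8 h after start" of the study infusion, and the difference between the after and before values. The paired test is then described as serving to "test if there is a significantly different amount of urine secreted while receiving BMS-986231 versus placebo". The bar-plot sentence also names urinary output.
- **SAP 15.3.** It summarizes urine furosemide, plasma furosemide and "the ratio of urinary sodium to urinary furosemide at 8 h by treatment", and adds paired plots. It contains no test.
- **Population.** Protocol 9.4.1.2 uses the randomized population for secondary efficacy. SAP 9.0 and 15.2 use the per-protocol set. SAP Appendix 4 uses per protocol for Tables and Figures 14.2.2.x and randomized for 14.2.4.x.
- **Declaration.** SAP 3.0 says that the SAP supersedes the protocol's statistics and that substantial differences will be identified. SAP 7.1 says there are none.

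**The concern.** FeNa, FeK and the sodium/furosemide ratio are the endpoints that would explain a urine-output effect. Followed literally, SAP 15.2 repeats the urine-volume comparison of SAP 15.1 and never tests FeNa or FeK at the time at which SAP 5.2.1 defines them. Three tests that the protocol most naturally calls for are absent, and the analysis set has changed. Because SAP 7.1 declares nothing, a reader who compares the study report with the protocol could not tell a planned choice from one made later.

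**Working it through.** The plan states no figure to reproduce here. The check compares the passages and counts what they contain.

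**1. Which quantities are at 8 h?**

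| Endpoint | Protocol 9.3.2 / SAP 5.2.1 | Protocol 8.1.2 | SAP analysis section | Test in SAP text |
|---|---|---|---|---|
| FeNa | 8 h | 4-8 h | 15.2: four window quantities | worded as urine volume |
| FeK | 8 h | 4-8 h | 15.2: four window quantities | worded as urine volume |
| Urine furosemide | 8 h | not covered | 15.3: 8 h | none |
| Plasma furosemide | 8 h | not covered | 15.3: 8 h | none |
| Sodium/furosemide ratio | 8 h | 4-8 h | 15.3: 8 h | none |

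SAP 15.2 gives 4 quantities x 2 ions = 8. None is a value at 8 h. The window covering 8 h from the start of infusion is not one either: it includes the 4 h before furosemide, whereas Protocol 9.4.1.2 calculates values at time points within the 4 h after the bolus and then analyses the 8-h point. By-interval bar charts could display a 7-8 h value but would not test it.

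**2. When does the first SAP 15.2 quantity match Protocol 8.1.2?** With the bolus at H4, the 4 h after furosemide are clock hours 4-8 and the two agree. Under Protocol 6.4, after an interruption and restart, "furosemide will be administered after at least 4 hours of effective study drug infusion". A 1-h interruption before H4 therefore puts the bolus at 4 + 1 = H5 or later. Clock 4-8 h then holds at most 8 - 5 = 3 post-bolus hours and at least 1 pre-bolus hour, so the two windows differ.

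**3. What is tested?** The SAP 15.2 test sentence repeats that of SAP 15.1. Appendix 4 lists Table 14.2.2.3 as a statistical analysis of fractional excretion, so such a test was meant. No visible passage says which of the four quantities per ion it uses.

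**4. Can a fractional excretion be totalled?** For ion X over a window,

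FE = 100 x (sum of U_X V / sum of U_cr V) x (P_cr / P_X),

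where U is urine concentration, V is urine volume and P is plasma concentration. This is a ratio and does not add across intervals. Protocol Table 8 has two collection intervals before furosemide and four after. If every interval had the same value f, adding percentages would give 2f before, 4f after and a difference of 2f with no change at all. Pooling amounts gives f, f and 0. The SAP does not say that percentages are added, but it does not exclude it.

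**5. How many protocol tests remain?** The protocol plan is 5 endpoints x 1 time = 5 paired tests. SAP 15.3 and Appendix 4 (Table 14.2.4.1, Figure 14.2.4.2) show 0 of 3 for urine furosemide, plasma furosemide and the ratio. The other two have a listed table with an unnamed quantity.

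**6. What does the population change do?** A paired test needs both periods, and SAP 8.1.2 imputes nothing unless noted. For the tests, the two sets therefore differ only in patients with values in both periods who did not complete per protocol. How many there would be is not known.

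**7. What does restoring the tests cost?** With five unadjusted tests at 0.05, the chance of at least one false positive is 1 - 0.95^5 = 22.6% under independence and 5% under full dependence. FeNa and the ratio share urine sodium, so independence does not hold.

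**The case against.** - **The SAP follows one of two protocol definitions.** This stands. The first SAP 15.2 quantity agrees with Protocol 8.1.2 when the bolus is at H4. A reader might infer that the SAP invented its window; the documents do not support that, because the conflict starts in the protocol. It does not rescue SAP 5.2.1, which keeps 8 h.
- **The 8-h value is itself undefined.** This stands. Neither document says which urine interval and plasma sample make it up; 7-8 h urine with H8 plasma is only a plausible reading.
- **The table shells may name the tested quantity and the formula.** They are a separate document and were not available, so this is possible. A reader might infer that the choice will be made after the data are seen. That goes too far: SAP 3.0 requires a signed SAP for database lock, and Table 14.2.2.3 is listed in advance. SAP 3.0 does, however, allow later changes without an updated SAP.
- **A similar analysis need not mean a t-test.** Protocol 9.4.1.1 also covers summaries, so the paired test is an inference. It is the natural one, being the only inferential method there.
- **Redaction might hide the tests.** This is unlikely. The SAP contents list shows the redacted block after 15.3 as a separate entry, and the legible Appendix 4 has no test table for these three endpoints.
- **A delayed bolus might seem to leave the post-bolus window without samples.** The documents do not support this as a fact. The footnotes to Protocol Tables 7 and 8 move the end-of-infusion samples when the infusion ends late, and the Na/K/creatinine sample is scheduled at H8 or end of infusion.
- **SAP Appendix 3 says its blood-sampling table covers Na and K, yet the table omits H7.** This is inherited from Protocol 8.5.1 and Table 7, so it is not a SAP departure.

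**Conclusion.** The concern holds as an inconsistency in the written plan. SAP 15.2 has 0 of 8 quantities at the 8 h that SAP 5.2.1 specifies, and 0 of 8 named as the one tested. The visible text has 0 of 3 paired tests for the furosemide and ratio endpoints. The secondary population differs between protocol and SAP, and within the SAP. SAP 7.1 declares none of this.

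The counts assume that 8 h means a value at that time point rather than a window, and that a similar analysis includes the paired t-test. A reader might infer that FeNa and FeK will not be tested at all, or that a treatment effect would be distorted by a known amount. Table 14.2.2.3 argues against the first. For the second, the documents give no time course of FeNa or FeK under treatment, so no size can be stated. These are secondary endpoints and the primary analysis is untouched. The sponsor should correct this before database lock.

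**What to change.** Before database lock:

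1. Reconcile 8 h with 4-8 h across Protocol 8.1.2, 9.3.2 and 9.4.1.2 and SAP 5.2.1, 15.2 and 15.3. Name one tested quantity per ion. If 8 h is kept, state which urine interval and plasma sample define it (for example 7-8 h urine with H8 plasma) and make the window values descriptive.
2. Reword the test and bar-plot sentences of SAP 15.2 so that they name FeNa and FeK.
3. State that any window value is computed from pooled urine amounts of the ion and of creatinine with a pre-stated plasma average, and not by adding interval percentages. How plasma is averaged is the sponsor's choice.
4. Restore the paired tests with 95% confidence intervals for urine furosemide, plasma furosemide and the ratio as unadjusted secondary tests, or declare these endpoints descriptive.
5. List every departure in SAP 7.1, including the secondary population, and align SAP 9.0, 15.2 and Appendix 4.

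Cost: if 8 h is kept, SAP wording, a clarification of Protocol 8.1.2 and minor programming on samples already scheduled. Choosing the window instead would also change Protocol 9.3.2 and 9.4.1.2 after randomization has begun. Restoring all tests leaves up to five unadjusted secondary p-values, which should be reported as such.
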